9.2. Adverse Events

The definitions of an AE or SAE can be found in [Appendix 4](#).

AEs will be reported by the participant or noted by the investigator.

The investigator and any designees are responsible for detecting, documenting, and recording events that meet the definition of an AE or SAE and remain responsible for following up AEs that are serious, considered related to the study treatment or study procedures, or that caused the participant to discontinue the study treatment (see [Section 8](#)).

9.2.1. Time Period and Frequency for Collecting AE and SAE Information

All AEs and SAEs will be collected from the signing of the Informed Consent Form (ICF) until 30 days after the final visit in the study (Visit 8) or Early Termination Visit, at the time points specified in the SoA ([Section 2](#)). Ongoing AEs at the end of study RLM-MD-01 and RLM-MD-02, and new AEs that occur after the signing of the ICF for RLM-MD-03 are considered to be AEs in RLM-MD-03.

Relamorelin

All SAEs will be recorded and reported to the sponsor or designee within 24 hours, as indicated in [Appendix 4](#). The investigator will submit any updated SAE data to the sponsor within 24 hours of it being available.

Investigators are not obligated to actively seek AE or SAE in former study participants. However, if the investigator learns of any SAE, including a death, at any time after a participant has been discharged from the study, and he/she considers the event to be reasonably related to the study treatment or study participation, the investigator must promptly notify the sponsor.

The method of recording, evaluating, and assessing causality of AEs and SAEs and the procedures for completing and transmitting SAE reports are provided in [Appendix 4](#).

9.2.2. Method of Detecting AEs and SAEs

Care will be taken not to introduce bias when detecting AEs and/or SAEs. Open-ended and non-leading verbal questioning of the participant is the preferred method to inquire about AE occurrences.

9.2.3. Follow-up of AEs and SAEs

After the initial AE/SAE report, the investigator is required to proactively follow each participant at subsequent visits/contacts. All AEs/SAEs and non-serious AEs of special interest ([AESI] as defined in [Appendix 4](#)) will be followed until resolution, stabilization, until the event is otherwise explained, or the participant is lost to follow-up (as defined in Section 8.3). Further information on AE/SAE follow-up procedures is given in [Appendix 4](#).

9.2.4. Regulatory Reporting Requirements for SAEs

- Prompt notification by the investigator to the sponsor of a SAE is essential so that legal obligations and ethical responsibilities towards the safety of participants and the safety of a study treatment under clinical investigation are met.
- The sponsor has a legal responsibility to notify both the local regulatory authority and other regulatory agencies about the safety of a study treatment under clinical investigation. The sponsor will comply with country-specific regulatory requirements relating to safety reporting to the regulatory authority, institutional review boards (IRB)/Independent Ethics Committees (IEC), and investigators, including the head of the study center if required.
- Investigator safety reports must be prepared for suspected unexpected serious adverse reactions (SUSAR) according to local regulatory requirements and sponsor policy and forwarded to investigators as necessary.

Relamorelin

- An investigator who receives an investigator safety report describing a SAE or other specific safety information (eg, summary or listing of SAEs) from the sponsor will review and then file it along with the investigator's brochure and will notify the IRB/IEC, if appropriate according to local requirements.

9.2.5. Pregnancy

- Details of all pregnancies in female participants and female partners of male participants will be collected after the start of study treatment and until 7 days after the last dose.
- If a pregnancy is reported, the investigator should inform the sponsor within 24 hours of learning of the pregnancy and should follow the procedures outlined in Section 12.5.
- Abnormal pregnancy outcomes (eg, spontaneous abortion, fetal death, stillbirth, congenital anomalies, ectopic pregnancy) are considered SAEs.

9.2.6. Medical Device Incidents (Including Malfunctions)

Medical devices are being provided for use in this study for the purpose of study medication self-administration. In order to fulfill regulatory reporting obligations worldwide, the investigator is responsible for the detection and documentation of events meeting the definitions of incident or malfunction that occur during the study with such devices.

The definition of a Medical Device Incident can be found in [Appendix 7](#).

NOTE: Incidents fulfilling the definition of an AE/SAE will also follow the processes outlined in Section 9.2 and [Appendix 4](#) of the protocol.

9.2.6.1. Time Period for Detecting Medical Device Incidents

- Medical device incidents or malfunctions of the device that result in an incident will be detected, documented, and reported during all periods of the study in which the medical device is used.
- If the investigator learns of any incident at any time after a participant has been discharged from the study, and such incident is considered reasonably related to a medical device provided for the study, the investigator will promptly notify the sponsor.

The method of documenting Medical Device Incidents is provided in [Appendix 7](#).

Relamorelin

9.2.6.2. Follow-up of Medical Device Incidents

- All medical device incidents involving an AE will be followed and reported in the same manner as other AEs (see Section 9.2). This applies to all participants, including those who discontinue study treatment.
- The investigator is responsible for ensuring that follow-up includes any supplemental investigations as indicated to elucidate the nature and/or causality of the incident.
- New or updated information will be recorded on the originally completed form with all changes signed and dated by the investigator.

9.2.6.3. Prompt Reporting of Medical Device Incidents to Sponsor

- Medical device incidents will be reported to the sponsor within 24 hours after the investigator determines that the event meets the protocol definition of a medical device incident.

9.2.6.4. Regulatory Reporting Requirements for Medical Device Incidents

- The investigator will promptly report all incidents occurring with any medical device provided for use in the study in order for the sponsor to fulfill the legal responsibility, if needed, to notify appropriate regulatory authorities and other entities about certain safety information relating to medical devices being used in clinical studies.
- The investigator, or responsible person according to local requirements (eg, the head of the medical institution), will comply with the applicable local regulatory requirements relating to the reporting of incidents to the IRB/IEC.

9.2.7. Adverse Events of Special Interest**9.2.7.1. Hy's Law**

Study site personnel must report every participant who meets potential Hy's Law criteria which are as follows:

- Alanine aminotransferase (ALT) or aspartate aminotransferase (AST) $\geq 3 \times$ upper limits of normal (ULN) AND
- Total bilirubin $\geq 2 \times$ ULN AND
- Alkaline phosphatase $< 2 \times$ ULN

Typically, all analytes will be obtained from the same sample, but they may come from multiple samples taken within a 24-hour period. This requirement applies from the time the participant

Relamorelin

signs the ICF for the study until 30 days after the final protocol-defined study visit or the last known dose of study treatment (if the final visit does not occur).

A laboratory alert for potential Hy's laws cases will be in place. Investigators and the sponsor must be immediately notified when the above criteria have been met. [REDACTED]

Every effort to determine the cause of the liver enzyme abnormalities must be made, and close monitoring should be initiated in conjunction with the MSP and in accordance with the [FDA Guidance for Industry, Drug-Induced Liver Injury: Premarketing Clinical Evaluation, July 2009](#).

Additional details regarding liver safety assessments and follow up are provided in [Appendix 6](#).

9.2.7.2. Inadequate Control of Diabetes: Hyperglycemia and Hypoglycemia

The irregular and delayed emptying of the stomach in DG has a major effect on the presentation of ingested carbohydrate to the small intestine for absorption, complicating the dosing of hypoglycemic agents (including insulin) used to manage glycemia. Participants should be closely monitored for changes to their diabetes control while in the study, and events related to hyperglycemia or hypoglycemia that are considered to be clinically significant should be reported as AEs (Section [9.2.1](#)).

9.2.7.3. Major Adverse Cardiovascular Events

Patients with DG typically have long-standing diabetes mellitus, which predisposes them to develop macrovascular (and microvascular) complications. These include Major Adverse Cardiovascular Events (MACE) commonly defined as death from cardiovascular causes, non-fatal myocardial infarction, non-fatal stroke, and often also including revascularization (coronary or peripheral) procedures, and hospitalization for unstable angina pectoris.

In this study, occurrence of any of these events should be reported to the MSP within 24 hours of being made aware on the SAE form, followed by a complete report including narrative description of the event, test results, and copies of hospital records, if applicable. All reports of possible MACE will be adjudicated internally in a blinded fashion by a committee of qualified physicians on a periodic basis depending on the frequency of reported events. The functioning of the committee will be governed by charter.

Relamorelin

9.2.8. Medication Errors

Medication error refers to any unintended error in the dosing and/or administration of the study treatment as per instructions in the protocol. Medication errors generally fall into 4 categories as follows:

- Wrong study drug/device
- Wrong dose (including dosing regimen, strength, form, concentration, amount)
- Wrong route of administration
- Wrong participant (ie, not administered to the intended participant)

Medication errors include occurrences of overdose and underdose of the study treatment.

Overdose: Unintentional administration of a quantity of the study treatment given per administration or per day that is above the maximum recommended dose (10 µg BID or 20 µg/day) according to the reference safety information or protocol for the study treatment or comparator as applicable. This also takes into account cumulative effects due to overdose.

Underdose: Unintentional administration of a quantity of the study treatment given per administration or per day that is under the minimum recommended dose according to the reference safety information or protocol. Since there is no clinical information on the efficacy of relamorelin at a dose less than 10 µg BID, a dose of 10 µg once daily should be considered an underdose.

9.3. Treatment of Overdose

For this study, any dose of study treatment greater than 150 µg BID within a 24-hour time period will be considered an overdose.

The sponsor does not recommend specific treatment for an overdose.

In the event of an overdose, the investigator should:

1. Contact the MSP immediately.
2. Closely monitor the participant for any AE/SAE and laboratory abnormalities until study treatment can no longer be detected systemically.
3. Document the quantity of the excess dose as well as the duration of the overdose in the site's source documents for the participant.

Relamorelin

Decisions regarding dose interruptions or modifications will be made by the investigator in consultation with the MSP based on the clinical evaluation of the participant.

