3.2. Background

Relamorelin is being developed for the treatment of patients with DG to address the existing unmet need for an effective and safe/tolerable treatment, attested to by the FDA's granting of fast-track designation to relamorelin for the treatment of DG in adults. It is a member of an established class of compounds, ghrelin agonists, but if granted regulatory approval, will be the first member of this class to attain marketing approval.

In clinical studies to date, 466 participants with T1DM or T2DM with DG have been exposed to relamorelin at doses up to 100 µg administered twice daily (BID) by subcutaneous (SC) injection for 12-weeks.

In a randomized, placebo-controlled, multiple-dose Phase 2a study (RM-131-004), participants with T1DM and T2DM and DG received 28 days of double-blind treatment with relamorelin. GE was accelerated and compared to placebo, relamorelin 10 µg BID significantly decreased the vomiting severity score and mean number of weekly vomiting episodes in participants with vomiting at baseline and produced improvement in the 4 individual DG symptoms of nausea, abdominal pain, bloating and early satiety as well as significant improvement in the composite endpoint of the 4 symptoms ($p = 0.043$). The safety and tolerability profile of relamorelin in Study RM-131-004 was generally good.

The results in Study RM-131-004 helped the sponsor select the target patient population for enrollment in the Phase 2b Study RM-131-009, DG participants with vomiting at baseline, and encouraged assessment of a wider range of relamorelin doses.

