5.5. Justification for Dose

Study RM-131-009 was a 12-week Phase 2b, randomized, double-blind, placebo-controlled, parallel group study to evaluate the safety and efficacy of relamorelin in diabetic participants with moderate to severe DG. The doses included within the study were 10 µg BID, 30 µg BID, and 100 µg BID. In general, all doses tested within RM-131-009 appeared to demonstrate meaningful reductions in overall DG symptom scores including vomiting episodes, with acceptable safety and tolerability. The frequency of vomiting episodes was reduced from baseline over the 12-week treatment period to a similar extent for participants who received the 3 doses of relamorelin tested and placebo. Based upon the observed dose response of change-from-baseline symptom scores collected daily over the course of 12 weeks using the DGSSD, the 30 µg BID, and 100 µg BID doses demonstrated apparent maximal effects, while the 10 µg BID dose achieved near maximal reductions. Of note, the twice-a-day regimen of relamorelin appears to be necessary for effective symptom relief; the 10 µg once daily study treatment did not demonstrate significant improvement in symptom relief compared to placebo after 28 days of dosing in Study RM-131-004.

Review of the safety laboratory data collected in RM-131-009 revealed an apparent dose-related increase in HbA1c values. Although the variability in HbA1c response was high across all treatments, the 30 µg BID and 100 µg BID doses demonstrated apparent maximal changes in HbA1c values, while the 10 µg BID dose resulted in an approximately half-maximal increase after 12 weeks of study. Shorter durations of treatment (4 weeks) with 10 µg BID of relamorelin, as observed in Study RM-131-004, did not demonstrate this apparent increase in HbA1c in diabetic participants.

Based on the efficacy and safety data, the relamorelin dose selected for this study is 10 µg BID.

Relamorelin

6. Study Population

Prospective approval of protocol deviations to recruitment and enrollment criteria, also known as protocol waivers or exemptions, is not permitted.

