7.6. Treatment Compliance

Study treatment compliance will be closely monitored by assessing the participant's daily reporting of self-administered study treatment on the electronic hand-held device. Before dispensing new study treatment, study site personnel will make every effort to collect all unused study treatment.

The study centers will keep an accurate drug disposition record that specifies the amount of study treatment dispensed to each participant and the date of dispensing.

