9.5. Pharmacokinetics

Pharmacokinetic parameters are not evaluated in this study.

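### Sections 9.2.8 and 9.3 give overdose limits 15-fold apart, and the response steps sit only under the higher one, so a site may not apply them after one accidental extra 10 µg injection.

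*Protocol*

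**What the plan says.** Two adjacent protocol sections define overdose.

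- **Section 9.2.8, Medication Errors.** Overdose is the unintentional administration of a "quantity of the study treatment given per administration or per day that is above the maximum recommended dose". That maximum is given as 10 µg BID or 20 µg/day. The section classifies the error but prescribes no action.
- **Section 9.3, Treatment of Overdose.** For this study, "any dose of study treatment greater than 150" µg BID within a 24-hour period is considered an overdose. The steps follow under the words "In the event of an overdose, the investigator should": contact the medical safety physician (MSP) at once, watch closely for adverse events and laboratory abnormalities, and record how large the excess was and how long it lasted.

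Neither section cites the other, and neither describes a lower and a higher tier. The SAP does not define overdose.

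**The concern.** One word has two operative meanings, and the instructions attached to it sit beneath only one of them. The error that the higher limit leaves out is an everyday one for a self-injected, twice-daily pen: a participant forgets a dose was taken and injects again. Under 9.2.8 that is an overdose. Under the definition that opens 9.3 it is not.

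Sites that read the two sections differently could handle the same event differently. One would call the MSP and document the excess; another would do neither. What is at stake is consistent safety handling and a complete record of dosing errors. No efficacy endpoint or analysis depends on it.

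**Working it through.** The protocol states no derived figure to reproduce. The check is a comparison of the two definitions with simple dose arithmetic.

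**Inputs**
- Scheduled dose: 10 µg twice daily (Table 7-1), so 2 × 10 = 20 µg/day.
- Section 9.2.8 limit: 10 µg per administration, or 20 µg/day.
- Section 9.3 limit: 150 µg BID, read as 150 µg given twice, so 2 × 150 = 300 µg/day.
- Assumption: one injection delivers the 10 µg unit dose in Table 7-1.

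**Gap between the limits**
- Per administration: 150 / 10 = 15.
- Per day: 300 / 20 = 15.

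**One accidental extra injection**

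| Event | Amount | Section 9.2.8 | Section 9.3 |
|---|---|---|---|
| Third injection in the day | 3 × 10 = 30 µg/day | 30 > 20: overdose | 30 < 300: not an overdose |
| Two injections at one time | 2 × 10 = 20 µg | 20 > 10: overdose | 20 < 150: not an overdose |

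**Exposure for context**
- The Phase 2b study (Sections 3.2 and 5.5) tested 30 µg BID, or 60 µg/day. The example day is 30 / 60 = 50% of that.
- The highest dose reported was 100 µg BID, or 200 µg/day. The example day is 30 / 200 = 15% of that.

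**Do other provisions supply the missing steps?** I looked for any other text requiring an MSP call and a record of the excess after an accidental double dose without symptoms.
- Section 7.6 has "daily reporting of self-administered study treatment on the electronic hand-held device". This serves compliance monitoring and triggers no call.
- The opening of Section 9 sends safety concerns to the sponsor immediately, but does not say that a small excess is such a concern.
- Sections 9.2.7.2 and 9.4.5 cover diabetes control and home glucose checks.
- Section 12.4.1 makes symptoms of a suspected overdose reportable. The overdose itself is reportable only if intentional with possible self-harm.
- Sections 9.2.6.3 and 12.7 require device incidents to be reported within 24 hours. A harmless double dose caused by the user would not ordinarily meet the incident definition.

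Each narrows the gap. None closes it.

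**The case against.** The strongest reply is that the steps in 9.3 carry no qualifier. They begin "In the event of an overdose, the investigator should", and the section just before has already called anything above 10 µg BID or 20 µg/day an overdose. A site that reads both can apply the steps. That stands, so the consequence must be put as a possibility. A reader might infer that sites will fail to act after a small overdose. The documents do not support that: they permit either reading and give no information on site behaviour or on how often dosing errors occur.

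A second reply is that the difference may be deliberate, with a low limit for classifying errors and a high one for clinical management. The section titles fit this. But 9.3 words its limit as the study's definition, not as an escalation point, and nothing says that tiers are intended. If they are, the text should say so.

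A third reply is that the clinical stakes are small, and this also stands. Section 3.2 reports that participants with diabetic gastroparesis "have been exposed to relamorelin at doses up to 100" µg twice daily for 12 weeks, and Section 5.5 describes the tested doses in general as coming "with acceptable safety and tolerability". A reader might infer from a 15-fold gap that participants face a material hazard. The ratio compares two limits and does not measure harm. The one caution is that Section 5.5 also reports an apparent dose-related rise in HbA1c.

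The summary of changes mentions removal of a 150 µg BID statement from 9.2.8. The point does not rest on that; it rests on the two current sections.

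**Conclusion.** The point holds as a minor safety-procedure correction. That the two definitions conflict is certain: both are current, they differ 15-fold, and neither refers to the other. That a site would omit the steps after a small overdose is possible, not shown.

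The example rests on 10 µg per injection and on reading 150 µg BID as two doses of 150 µg. The frequency of dosing errors is not given, so no count of affected participants can be offered. Endpoints, power and analysis are untouched. The SAP (Section 4) says the study ended early, so the practical value now lies in a correct protocol record and in any reuse of this text.

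**What to change.** In Section 9.3, delete the sentence containing the 150 µg BID limit and put in its place:

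*An overdose is any administration above 10 µg or any daily total above 20 µg. This includes the unintentional overdoses defined in Section 9.2.8 and also intentional ones.*

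The second sentence is needed because 9.2.8 covers only unintentional excess, whereas Section 12.4.1 requires an intentional overdose with possible self-harm to be reported. Without it, the two sections would still differ with no explanation.

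At that limit, require MSP contact and documentation of the excess. For small excesses, let the investigator decide the extent of adverse-event and laboratory monitoring with the MSP. Full monitoring after every extra 10 µg would be out of proportion to the exposure shown above, and 9.3 already has dose-interruption decisions made in consultation with the MSP.

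The cost is a few sentences in one section and some extra MSP calls.

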9.4. Safety Assessments

Planned timepoints for all safety assessments are provided in the SoA (Section 2).

9.4.1. Physical Examinations

Complete physical examinations (excluding pelvic exam in women and genital exam in men, and rectal exam in both genders) are to be performed. Symptom-directed (abbreviated) physical examinations, including evaluation of the injection sites for clinically significant reactions, will be conducted as required at other study visits.

Participants should be weighed with no shoes, in light clothing, without any outerwear at the visits indicated on the SoA (Section 2); height to be measured only at Visit 1 of lead-in study RLM-MD-01 or RLM-MD-02.

Any abnormality noted during the physical examination performed at Visit 7 (or an early termination visit that occurs prior to Visit 7) that was not present during the physical examination at Visit 1 should be reported as an AE if considered by the investigator to be clinically significant. Any abnormality noted during the physical examination performed at Visit 8 (or an early termination visit that occurs after Visit 7) that was not present during the physical examination at Visit 7 should be reported as an AE if considered by the investigator to be clinically significant.

